SIGNATURE PAGE	ii
LIST OF CONTENTS	iii
KEY STUDY CONTACTS	iv
STUDY SUMMARY	iv
FUNDING	v
ROLE OF SPONSOR AND FUNDER	v
PROTOCOL CONTRIBUTORS	vi
STUDY FLOW CHART	vii
STUDY PROTOCOL	
1. BACKGROUND	1
2. RATIONALE	2
3. THEORETICAL FRAMEWORK	3
4. RESEARCH QUESTION/AIM(S)	4
5. STUDY DESIGN/METHODS	5
6. STUDY SETTING	5
7. SAMPLE AND RECRUITMENT	6
8. ETHICAL AND REGULATORY COMPLIANCE	8
9. DISSEMINATION POLICY	11
10. REFERENCES	11
11. APPENDICES	12

KEY STUDY CONTACTS

Chief Investigator	[name] Lead Respiratory Physiologist Hampshire Hospitals NHS Foundation Trust [name] Email: [contact]
Principle Investigator	[name] Trainee Clinical Scientist Hampshire Hospitals NHS Foundation Trust [name] Email: [contact]
Academic Supervisor (MSc Project for [name])	[name] Professor of Motor Neuroscience Faculty of Science and Engineering [name] Manchester Metropolitan University [name] Email: [contact]
Academic advisor	[name] Faculty Head of Research and Knowledge Exchange, Health and Wellbeing University of Winchester [name] Email: [contact]
Study Co-ordinator	[name]
Sponsor	Hampshire Hospitals NHS Foundation Trust [name]
Funder(s)	Hampshire Hospitals NHS Foundation Trust [name]

STUDY SUMMARY

Study Title	Comparison of the standard Maximal 6-Minute Walk Test against a Normal-speed 6-Minute Walk Test as an alternative and accurate assessment for ambulatory oxygen requirement.
Internal ref. no. (or short title)	Maximal-speed vs Normal-speed 6MWT for ambulatory oxygen assessment.
Study Design	Randomised crossover trial of patients referred for a standard Maximal 6-Minute Walk Test (Max_6MWT) where half of patients will perform the standard Max_6MWT followed by a Normal-speed 6-Minute Walk Test (Nor_6MWT) and the other half a Nor_6MWT followed by Max_6MWT.

Study Participants	Any patient referred for a Max_6MWT with capacity to consent, >18 years of age and able to perform a Max_6MWT.
Planned Size of Sample (if applicable)	82
Follow up duration (if applicable)	N/A
Planned Study Period	18 – 24 months
Research Question/Aim(s)	Does Nor_6MWT provide a better indicator for ambulatory oxygen requirement than the standard Max_6MWT

FUNDING AND SUPPORT IN KIND

FUNDER(S) (Names and contact details of ALL organisations providing funding and/or support in kind for this study)	FINANCIAL AND NON FINANCIAL SUPPORT GIVEN

1 BACKGROUND

Patients with lung disease who report breathlessness on exertion are often referred for a Max_6MWT. During this test patients are asked to walk up and down a corridor (or other flat area) for six minutes whilst their blood oxygen levels and heart rate are non-invasively measured using a pulse oximeter (finger probe) and the distance walked is measured. In addition, a questionnaire that obtains a Borg Score measures the patients' perceived breathlessness and leg muscle fatigue both before and immediately following the test.

A Max_6MWT provides clinicians with two primary results. Firstly, they determine whether the patient's blood oxygen levels decline whilst they walk which is used to help determine whether they could benefit from ambulatory oxygen therapy. Ambulatory oxygen therapy involves walking with a cylinder of compressed oxygen or a portable oxygen concentrator which the patient breathes from via a face mask or nasal cannula. Secondly, they provide a total distance walked which provides a measurement of functional capacity and physical impairment.

The standardised approach for a Max_6MWT as recommended by international and UK respiratory bodies and used by our department is to ask the patient to walk as far as possible during the six minutes and thus essentially walk as fast as possible¹. A Max_6MWT is therefore appropriate to assess the patient's maximal walking distance and thus functional capacity which is useful for assessing the impact of a patient's lung disease on their quality of life and is also used by surgeons and anaesthetists to assess surgical risk. However, it would seem likely that a significant number of patients will demonstrate a decline in blood oxygen levels that they may never experience in their daily life when they walk at their normal and slower pace. Subsequently they may be incorrectly prescribed ambulatory oxygen therapy or prescribed ambulatory oxygen at a flow rate exceeding what is required and possibly safe.

We are aware that many oxygen services across the UK, including some in Hampshire, will assess patients for ambulatory oxygen by having them perform their normal day-to-day activities whilst measuring their oxygen levels, rather than performing a Max_6MWT. These include activities such as walking up and down the stairs, walking around their house/garden etc. This seems a far more appropriate assessment for ambulatory oxygen, but a thorough literature review was unable to find any studies that had investigated whether a Max_6MWT caused a greater reduction in blood oxygen levels than occurs during these normal day-to-day activities. Until the current guidelines are challenged with evidence to show a Max_6MWT may not be an appropriate tool to assess patients for

ambulatory oxygen most departments will continue to follow national and international recommendations and use a Max_6MWT.

In this study, patients who are routinely referred for a Max_6MWT to investigate possible exercise-induced hypoxaemia will be invited to perform an additional walking test which is performed at their normal walking speed, referred here on in as a Nor_6MWT. This additional test will utilise the exact same medical equipment to record their blood oxygen levels as that of the Max_6MWT and be performed at the same location (i.e. flat hospital corridor). The order of performing these tests will be randomised with half performing the Max_6MWT first and the other half performing the Nor_6MWT first. Patients will be given 20 minutes to rest between each test in line with the British Thoracic Society guidelines, or a minimum of 10 minutes with a return to baseline of SpO₂, HR and Borg Scores.

2 RATIONALE

- The routinely used and internationally recognised diagnostic test for assessing the requirement of ambulatory oxygen, Max_6MWT may not correspond to the degree of exercise that patients actually perform when they would use their prescribed ambulatory oxygen (i.e. normal walking speed).
- It is possible that a significant proportion of patients prescribed ambulatory oxygen cannot physiologically benefit from using it as they do not experience a decline in oxygen levels during their normal physical exercise.
- Prescribing of ambulatory oxygen to patients that cannot benefit from it carries additional burdens for the patient, and costs for the NHS, without improving the patient's quality of life.
- If this study shows that a normal walking speed test is a more appropriate assessment for ambulatory oxygen, a higher proportion of patients prescribed ambulatory oxygen will benefit from the therapy and reduce incorrect prescribing of ambulatory oxygen.
- Max_6MWT is a maximal exercise test for most patients with notable respiratory disease and is not always well tolerated (e.g. becoming very breathless). Furthermore, it carries a small but not insignificant risk of acute heart issues and falls. A 6 minute or shorter test at normal walking speed would be safer and easier for a patient to perform.
- Patients' wellbeing could be harmed by misdiagnosing exercise-induced hypoxaemia. Anecdotal evidence suggests some patients become less active after being prescribed ambulatory oxygen for a variety of reasons, including feeling self-conscious or struggling to carry the oxygen cylinder.
- Furthermore, patients may be worried about exercising without ambulatory oxygen if prescribed this therapy due to the perception of risk due to exercise-induced hypoxaemia and potentially incorrect requirement for supplemental oxygen.
- Patients who demonstrate exercise-induced hypoxaemia during a Max_6MWT are required to repeat the Max_6MWT at least once in order to identify the required flow rate of ambulatory oxygen. Titrating the flow of ambulatory oxygen is required to ensure it is sufficient to prevent the exercise-induced hypoxaemia but not too high that could induce hypoventilation and subsequent CO₂ retention. It is plausible that prescribing a flow rate shown to prevent hypoxaemia during a Max_6MWT could far exceed that required to prevent

hypoxaemia during a patients' normal day to day exercise activities and lead to CO₂ retention. Furthermore, prescribing at a higher than required flow rate will lead to reduced cylinder duration or reduced battery life of portable concentrators which in turn could lead to restraints in the duration patients could exercise for.

- In some cases, sub-maximal 6MWT are reported to be performed ² without rationale or comparison with the internationally recognised guidelines for a maximal-effort 6MWT ³. There is no published literature adapting the Max_6MWT to improve the suitability for ambulatory oxygen assessment.

3 THEORETICAL FRAMEWORK

Due to the nature of the Max_6MWT, patients are required to walk as far as they can in 6 minutes. This may lead to an inaccurate assessment of their requirement for ambulatory oxygen as this form of exercise may not correspond to their normal daily activities (such as walking to the shops, walking up the stairs, gardening). It may also not accurately measure the normal changes in oxygen saturation (or desaturation) that occurs in these patients during their normal daily activities.

These two problems could lead to the prescribing of ambulatory oxygen that does not assist patients in their normal daily activities and, therefore, is a burdensome and ineffective therapy for some individuals ⁴. Several studies have also shown that ambulatory oxygen is often prescribed with no measurable benefit to patients due to a variety of factors, including potentially inaccurate indications from investigations like 6MWTs. This appears to be exaggerated in patients with milder symptoms in diseases such as COPD, and potential benefits were negated when patients had to carry their supplemental oxygen supply ^{4,5}.

4 RESEARCH QUESTION/AIM(S)

To compare the nadir in oxygen saturation reached whilst performing a standard Max_6MWT compared with a Nor_6MWT.

To compare the average oxygen saturation and average drop in oxygen saturation from baseline to the nadir whilst performing a standard Max_6MWT compared with a Nor_6MWT.

To measure when the nadir in oxygen saturation occurs during a Nor_6MWT.

To assess in patients prescribed ambulatory oxygen, what benefit in their symptoms do they report and how does this compare to their Max_6MWT and Nor_6MWT results.

4.1 Objectives

Primary objective:

1. Average drop in SpO₂ from baseline to nadir

Secondary objectives:

1. Average SpO₂ during the 6 minutes walking
2. Nadir in oxygen saturation (SpO₂)
3. At what time does the nadir in SpO₂ occur during a Nor_6MWT

Other objectives:

1. Walking speed: Distance walked divided by 6 minutes
2. Average HR during the 6 minutes walking
3. Peak HR
5. Borg Scores
6. Results from questionnaires (for patient's prescribed ambulatory oxygen)

4.2 Outcome

A greater drop in oxygen saturation during a Max_6MWT compared with Nor_6MWT may indicate over-prescribing of ambulatory oxygen as during normal activity, patients' requirement for oxygen may be lower than indicated by a Max_6MWT. Whilst ambulatory oxygen can improve patients' quality of life, it is not without drawbacks and, therefore, prescribing only to patients that will benefit is important.

5 STUDY DESIGN and METHODS of DATA COLLECTION AND DATA ANALYSIS

Patients attending a routine appointment for a Max_6MWT will be identified and approached to be invited to participate in the research study.

Along with a basic clinical history, the patient's blood pressure, Borg score for dyspnoea and leg fatigue, oxygen saturation and heart rate will be recorded before the walk tests – their baseline measurement.

The order of the tests will be randomised using a random number generator on the day where odd numbers will perform a Max_6MWT followed by a Nor_6MWT and even numbers the reverse. For each test, clear instructions will be provided along with continuous monitoring of their oxygen saturation heart rate and distance walked for the 6 minutes of the test using a using a Bluetooth enabled device that transmits this data to a medically approved monitoring device with manual lap counting. Should this equipment fail, manual readings will be taken every minute during the test.

Between each test, ample time (usually 20 minutes) will be provided for a patient's degree of dyspnoea and leg fatigue, and objective measurements of heart rate and oxygen saturation to return to baseline.

From these tests it is possible to determine the distance walked, the degree of dyspnoea and leg fatigue, the time to nadir in oxygen saturation, the average drop in oxygen saturation and the average and peak heart rate. These data can be compared using paired tests to determine differences between Max_6MWT and Nor_6MWT.

Only the results of the clinical standard Max_6MWT will be relayed back to the referring member of the clinical care team – they will not see the outcome of the Nor_6MWT. A copy of the IPAQ Elderly Short questionnaire will be provided to fill out during the appointment – this forms the baseline assessment. If they decide to prescribe ambulatory oxygen, questionnaires will be provided to complete either in physical form, or over the phone with a member of the research team. These patients will be identified from the hospital digital patient record. These will include two identical copies of the IPAQ Elderly Short questionnaire – one before they begin ambulatory oxygen and one to complete after four weeks of using ambulatory oxygen – and an Ambulatory Oxygen Questionnaire four weeks after starting ambulatory oxygen. These will provide a surrogate for clinical benefit achieved by the use of ambulatory oxygen. The questionnaires will contain patient identifiable information to enable linking of the data to their test results and, therefore, will be stored securely on a NHS shared drive within HHFT. A secure nhs.net email will be used to receive the completed questionnaires if physical copies are not returned. These data, as a metric of clinical improvement, can then be compared with the outcomes of both the Max_6MWT and Nor_6MWT to determine if these tests can predict patients that will benefit from ambulatory oxygen.

The data from these tests will be stored on the clinical software used in routine testing (SentrySuite, Vyaire) and this may be exported to numerical handling software such as Excel (Microsoft) and stored internally on an NHS shared drive. Follow up will be limited to questionnaire data for those prescribed ambulatory oxygen and this will be arranged either by the physiology team or by the consultants prescribing ambulatory oxygen.

In the event a patient be randomised to the Nor_6MWT and declines to proceed to the Max_6MWT, the results from the Nor_6MWT will be passed on to the medical team and the patient will be withdrawn from the study.

5.1 6-minute walk test protocol

Steps for carrying out the walk test are outlined below:

Group 1: Maximal speed walking test (Max_6MWT) followed by normal speed walking test (Nor_6MWT).

Step 1: Wait at least 10 minutes in a seated position from any previous breathing tests. Baseline blood pressure, heart rate and oxygen saturation obtained. Borg score completed.

Step 2: Instructions provided: "

The aim of this test is to walk as far as possible for 6 minutes. You will walk along this hallway between the markers, as many times as you can in 6 minutes.

I will let you know as each minute goes past, and then at 6 minutes I will ask you to stop where you are. 6 minutes is a long time to walk, so you will be exerting yourself. You are permitted to slow down, to stop, and to rest as necessary, but please resume walking as soon as you are able.

Remember that the objective is to walk as far as possible for 6 minutes, but don't run or jog. "

Step 3: Very slow walk to the start line and then perform the walk test.

Step 4: Perform post-test Borg score immediately after the test. Twenty minutes of rest, or a minimum of 10 minutes sitting rest/recovery with a return to baseline of SpO₂, HR and Borg Score

Step 5: Proceed to perform Nor_6MWT as above but with the following instructions: "

The aim of this test is to walk at your normal walking speed for 6 minutes. This could be the speed that you walk a dog if you have one, or the speed you would walk around town shopping. You will walk along this hallway between the markers for 6 minutes.

I will let you know as each minute goes past, and then at 6 minutes I will ask you to stop where you are. 6 minutes is a long time to walk, so you will be exerting yourself. You are permitted to slow down, to stop, and to rest as necessary, but please resume walking as soon as you are able.

Remember that the objective is to walk at your normal walking speed for 6 minutes, but don't run or jog."

Step 6: Perform post-test Borg score immediately after the test. Allow the patient to rest for at least 10 minutes or until SpO₂ and HR back to baseline.

.....

Group 2: Nor_6MWT followed by Max_6MWT.

Step 1: Wait at least 10 minutes in a seated position from any previous breathing tests. Baseline blood pressure, heart rate and oxygen saturation obtained. Borg score completed.

Step 2: Instructions provided: "

The aim of this test is to walk at your normal walking speed for 6 minutes. This could be the speed that you walk a dog if you have one, or the speed you would walk around town shopping. You will walk along this hallway between the markers for 6 minutes.

I will let you know as each minute goes past, and then at 6 minutes I will ask you to stop where you are. 6 minutes is a long time to walk, so you will be exerting yourself. You are permitted to slow down, to stop, and to rest as necessary, but please resume walking as soon as you are able.

Remember that the objective is to walk at your normal walking speed for 6 minutes, but don't run or jog."

Step 3: Very slow walk to the start line and then perform the walk test.

Step 4: Perform post-test Borg score immediately after the test. Twenty minutes of rest, or a minimum of 10 minutes sitting rest/recovery with a return to baseline of SpO₂, HR and Borg Score

Step 5: Proceed to perform Max_6MWT with the following instructions: “

The aim of this test is to walk as far as possible for 6 minutes. You will walk along this hallway between the markers, as many times as you can in 6 minutes.

I will let you know as each minute goes past, and then at 6 minutes I will ask you to stop where you are. 6 minutes is a long time to walk, so you will be exerting yourself. You are permitted to slow down, to stop, and to rest as necessary, but please resume walking as soon as you are able.

Remember that the objective is to walk as far as possible for 6 minutes, but don't run or jog.”

Step 6: Perform post-test Borg score immediately after the test. Allow the patient to rest for at least 10 minutes or until SpO₂ and HR back to baseline.

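### A greater SpO2 drop on Max_6MWT than on Nor_6MWT would show a pace effect; with no SpO2 from daily activity, it would not by itself show over-prescribing or that Nor_6MWT is the better indicator

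*Combined protocol and SAP*

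**What the plan says.** The research question in the study summary is: "Does Nor_6MWT provide a better indicator for ambulatory oxygen requirement than the standard Max_6MWT".

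The measured comparison is narrower. One of the aims in Section 4 is to compare the "average drop in oxygen saturation from baseline to the nadir whilst performing a standard Max_6MWT compared with a Nor_6MWT", and Section 4.1 makes that drop the primary objective. Section 5 gives the analysis: "These data can be compared using paired tests to determine differences between Max_6MWT and Nor_6MWT". Section 1 says that the added walk will "be performed at the same location (i.e. flat hospital corridor" as the standard test.

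Section 4.2 then interprets the comparison: a greater drop on Max_6MWT than on Nor_6MWT "may indicate over-prescribing of ambulatory oxygen as during normal activity, patients' requirement for oxygen may be lower than indicated by a Max_6MWT".

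The protocol's own account of daily life is wider than level walking. Section 3 speaks of "normal daily activities (such as walking to the shops, walking up the stairs, gardening", and Section 1 also mentions stairs, house and garden. Section 1 adds that a literature search found no study setting Max_6MWT desaturation against desaturation in such activities.

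There is a second strand. The last aim in Section 4, the last of the other objectives in Section 4.1, and Section 5 plan to relate questionnaire results in patients prescribed oxygen to both walks, to see whether either test predicts benefit.

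**The concern.** Whether one test is a better indicator of requirement depends on how each relates to what happens in daily life, or to benefit from oxygen. The primary comparison contains neither. It measures how far SpO2 falls at two walking paces on the same level floor. Moving from that difference to over-prescribing requires the Nor_6MWT to represent normal activity. The study does not test that assumption, and the protocol's own list of daily activities does not fit it well.

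Suppose a patient drops less on Nor_6MWT than on Max_6MWT. Either the maximal test overstates what the patient meets in daily life, or the normal-pace test understates it because harder tasks such as stairs are left out. The two walks alone fit both accounts, so a larger Max drop cannot choose between them. Classifying each patient as positive or negative on each walk would not help either, because a patient positive on Max and negative on Nor fits both.

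What is at stake is the reading of the primary result. Maximal walking may well lower SpO2 more than slower walking. Section 8 expects the findings to bear on later clinical decisions, and the fourth bullet of Section 2 ties better-targeted prescribing to what this study shows. A significant pace difference could be reported as evidence of over-prescribing when the data fit the opposite account equally well.

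**Working it through.** **Inputs.** Section 7.2.1 gives 82 patients, an effect size of 0.30, 80% power and a type I error of 0.05. It does not state the kind of effect size or the sidedness. I take 0.30 as mean paired difference divided by the SD of the paired differences (d), and a two-sided test.

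**The plan's own figure.** On that reading the normal approximation gives n = ((1.960 + 0.842)/0.30)² = 87.2, so 88; the exact paired t-test gives 90. The stated 82 is not reproduced, and exact power at 82 is 76.6% rather than 80%. That is a separate matter and does not affect the argument here. I use 82 and 0.30 as stated.

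**Structure.** Let M, N and L be the mean drops on Max_6MWT, on Nor_6MWT and in daily activity. Write L = N + λ(M − N). Then:

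- overstatement by Max: M − L = (1 − λ)(M − N)
- understatement by Nor: L − N = λ(M − N)

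λ = 0 means daily life equals the Nor walk, λ = 1 means it equals the Max walk, and λ above 1 means it exceeds the Max walk. The documents give no daily-activity SpO2, so λ is unknown. The paired statistic uses only the observed Max-Nor differences, so λ does not enter it.

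**Chance of a significant result with Max above Nor, n = 82.** The noncentrality is d√82. At d = 0.30 it is 0.30 × 9.055 = 2.717, against a critical value of about 1.990 on 81 degrees of freedom, giving 76.6%.

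| d (Max − Nor) | Chance of significance, any λ |
|---|---|
| 0 | 2.5% |
| 0.15 | 26.8% |
| 0.30 | 76.6% |
| 0.50 | 99.4% |

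Simulation with 20,000 runs per cell at d = 0.30 gave 76.5%, 76.4%, 76.5% and 76.2% for λ = 0, 0.5, 1 and 1.5. These agree within simulation error, as they must.

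**For contrast.** Suppose the daily drop were measured and Max tested against it, with the same SD of paired differences (an assumption). The effect size would be (1 − λ) × 0.30:

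| λ | Effect size | Chance of significance, Max above daily |
|---|---|---|
| 0 | 0.300 | 76.6% |
| 0.25 | 0.225 | 52.1% |
| 0.5 | 0.150 | 26.8% |
| 0.75 | 0.075 | 9.9% |
| 1 | 0 | 2.5% |

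That comparison would respond to whether Max overstates daily desaturation. The planned one does not.

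**The case against.** **The questionnaires are a second source of evidence.** A reader might infer that the two corridor drops are all the study has. They are not. Under Section 5 only the Max result normally goes back to the referrer, so patients positive on Max and negative on Nor can be prescribed oxygen and followed up. Reported benefit in them would count against Nor, and its absence would support over-prescribing. This stands. It does not rescue Section 4.2, which argues from the SpO2 difference. The questionnaire comparison also has no control, analysis method, size or criterion, and its follow-up says nothing about patients who were not prescribed oxygen.

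**Section 4.2 is hedged.** A reader might infer a formal decision rule that takes the Nor walk as the truth. The text says only that a greater drop may indicate over-prescribing, and nowhere states that a significant test settles which indicator is better. This also stands. Even so, the hedge names no result that would point the other way.

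**The equal rates follow by construction.** True. They show what the comparison can distinguish; they are not an error rate. Nor is the test uninformative in every case: if pace has no effect, it is significant in this direction only 2.5% of the time.

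**Section 2 supports the stand-in.** Its first bullet equates exercise with prescribed oxygen with walking at normal speed. That is an assumption, narrower than the activities listed in Sections 1 and 3. Equally, nothing in the documents shows that patients do desaturate on stairs as far as on Max_6MWT; that remains only possible.

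**The change is partly redundant and the harm remote.** The Section 4 aims are already mostly descriptive, the Section 2 bullet is already conditional, and the study changes no prescribing criterion. This limits the seriousness. The summary question and Section 4.2 still go beyond the primary comparison.

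**Conclusion.** The concern holds as a mismatch between the primary comparison and the conclusion drawn from it. The paired test is a valid test of whether SpO2 falls further at maximal than at normal pace on the level. For any given non-zero gap, it is equally likely to be significant whether Max_6MWT overstates daily desaturation or Nor_6MWT understates it. With 82 patients that chance is about 77%, if 0.30 is a paired effect size and the test is two-sided. The equality itself rests on neither reading; it needs only that daily-activity SpO2 is absent from the comparison, which it is.

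The point is confined to what may be concluded from the SpO2 difference. It does not show that Max_6MWT is right about daily need or that Nor_6MWT misses need. It is worth correcting before results are reported, but calls for no change to design or conduct.

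**What to change.** Three wording changes:

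1. **Study summary.** State the primary question as whether the SpO2 drop from baseline to nadir is greater on Max_6MWT than on level walking at normal pace. Keep, as an exploratory question, how both tests relate to reported benefit in patients prescribed oxygen, so that the last aim in Section 4 stays within the study question.
2. **Section 4.2.** Say that a greater drop on Max_6MWT shows more desaturation than level walking at the patient's normal pace. Add that this does not by itself show that Max_6MWT overstates requirement in daily life, which includes stairs and other tasks not tested here, or that Nor_6MWT is the better indicator.
3. **Section 2, fourth bullet.** Make the statement about the suitability of a normal-pace test depend on evidence from daily activity or reported benefit, and not on the SpO2 difference alone.

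The cost is an amendment to the text: no added patients, procedures or data. The downside is a narrower headline claim.

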7.3 Recruitment

Once patients are referred for a standard Max_6MWT by a doctor at HHFT, patients will be made aware of the study by a covering letter and Patient Information Leaflet (PIL) alongside their routine appointment letter. At their outpatient appointment, the patient will again have the opportunity to review the PIL and ask any questions to the researcher(s) conducting the study. If they are willing to participate, informed consent will be taken during their appointment prior to testing. Accepting or refusing to participate in the study will have no impact on the care provided to the patient, or their ongoing clinical investigations and treatment.

If a patient is unable to complete both the Max_6MWT and Nor_6MWT, they will be subsequently removed from the study.

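### Walk order comes from an odd/even draw on the day with no independent list, timing rule or log, so a selectively repeated or overridden draw could not be detected

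*Combined protocol and SAP*

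**What the plan says.** Section 5 contains the protocol's only description of allocation: "The order of the tests will be randomised using a random number generator on the day where odd numbers will perform a Max_6MWT" first, and even numbers the reverse. The Background (section 1) gives the intended ratio: "The order of performing these tests will be randomised with half performing the Max_6MWT first and the other half performing the Nor_6MWT first". No blocking, separation by location, independent allocator, concealment or record of the number drawn is described.

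On timing, section 7.3 says "informed consent will be taken during their appointment prior to testing", but does not place the draw before or after consent, or before or after the Step 1 baseline in section 5.1.

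The primary objective (section 4.1) is "Average drop in SpO₂ from baseline to nadir". The analysis statement in section 5 is "These data can be compared using paired tests to determine differences between Max_6MWT and Nor_6MWT", with no order or period term.

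Three other provisions bear on the point:

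- **Decliners.** Section 5 covers the patient who has the normal-speed walk first and then stops: "declines to proceed to the Max_6MWT, the results from the Nor_6MWT will be passed on to the medical team and the patient will be withdrawn".
- **Incomplete pairs.** Section 7.3 says: "If a patient is unable to complete both the Max_6MWT and Nor_6MWT, they will be subsequently removed from the study".
- **Rest between walks.** Step 4 of section 5.1 requires "Twenty minutes of rest, or a minimum of 10 minutes sitting rest/recovery with a return to baseline of SpO₂, HR and Borg Score".

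**The concern.** Random order is this crossover's main protection against effects of walking second. As described, a reader of the final report could not tell whether the first number drawn was always used. Staff at the visit have the referral information (section 7.3.1) and the baseline readings, so they can form a view of who is likely to struggle.

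The plan also makes one order more convenient. A Max-first patient who stops after one walk has already done the referred test. A Nor-first patient who stops has not. That staff would act on this is an inference; the documents do not show it happening.

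If order did become linked to severity, and if walk 1 leaves fatigue or desaturation that deepens the fall on walk 2, the residual would fall unevenly on the two tests. The Max-minus-Nor difference would then be shifted, and the planned paired tests have no term to absorb any of the shift.

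**Working it through.** The plan gives no figure for this point, so there is nothing to reproduce. The check asks when selective ordering biases the contrast, and by how much under stated assumptions.

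**Model.** Let D be the fall in SpO₂ on the maximal walk minus the fall on the normal walk. Let τ be the true test effect and c the residual from walk 1 that adds to the fall on walk 2.

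- Max first: E[D] = τ − c.
- Nor first: E[D] = τ + c.

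For severity group s with population share f, residual c and probability p of Max first:

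- Unadjusted bias (mean of all D) = Σ f·c·(1 − 2p).
- Order-adjusted bias (equal-weight mean of the two sequence means, same τ for all) = ½ × (mean c in Nor-first − mean c in Max-first).

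With a fair draw, p = 0.5 in every group and both expressions are 0. Severity itself cancels, because each patient does both walks. If c is the same for everyone, the adjusted bias is 0 whatever p is.

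**Inputs, all assumed.** 30% of patients frail; c = 2 points in frail and 0.5 in other patients; p = 0.5 in other patients; SD of the within-patient difference 3 points. The 0.30 effect size is from section 7.2.1, which gives neither its metric nor an SD. Reading it as mean difference over SD gives a target of 0.30 × 3 = 0.9 points.

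**Half of frail Nor-first draws redrawn once.** A redraw gives Max first only half the time, so p = 0.5 + 0.5 × 0.5 × 0.5 = 0.625.

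- Unadjusted: 0.3 × 2 × (1 − 1.25) = −0.15.
- Frail share in Max-first: 0.1875/0.5375 = 0.349, mean c = 0.5 + 1.5 × 0.349 = 1.023.
- Frail share in Nor-first: 0.1125/0.4625 = 0.243, mean c = 0.865.
- Adjusted: ½ × (0.865 − 1.023) = −0.08.

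**Half of frail Nor-first draws switched outright.** p = 0.5 + 0.5 × 0.5 = 0.75.

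- Unadjusted: 0.3 × 2 × (1 − 1.5) = −0.30.
- Frail share in Max-first: 0.225/0.575 = 0.391, mean c = 1.087.
- Frail share in Nor-first: 0.075/0.425 = 0.176, mean c = 0.765.
- Adjusted: ½ × (0.765 − 1.087) = −0.16.

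| Ordering of frail patients | p | Unadjusted | Adjusted | Share of 0.9 |
|---|---|---|---|---|
| Draw followed as written | 0.5 | 0 | 0 | 0 |
| Half of Nor-first redrawn once | 0.625 | −0.15 | −0.08 | 17%, 9% |
| Half of Nor-first switched | 0.75 | −0.30 | −0.16 | 33%, 18% |
| Half of Max-first redrawn once | 0.375 | +0.15 | +0.08 | 17%, 9% |
| Half of Max-first switched | 0.25 | +0.30 | +0.16 | 33%, 18% |

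The bias is proportional to the residuals: halving them to 1 and 0.25 halves every entry. With no residual all entries are 0. The percentages fall as the assumed SD rises.

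**A second set of assumptions**, in SDs of D, to be read against 0.30. Half of patients are severe, and every severe patient who first draws Max is redrawn once, so p = 0.25 for severe and 0.5 for others.

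- Common residual 0.10: unadjusted +0.025, adjusted 0.
- Residual 0 in mild and 0.20 in severe: unadjusted +0.050, adjusted +0.027. If only 10% to 50% of those draws are redrawn, adjusted +0.003 to +0.013.
- No residual, τ of 0.2 in mild and 0.4 in severe: unadjusted 0, adjusted −0.007. Here the unequal sequences and the varying test effect produce the small bias.

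**Balance.** Separately, an unrestricted odd/even draw of 82 gives exactly 41/41 with probability 8.8%, and a split of 36/46 or worse with probability 32%. This is chance, not selection, but it bears on the stated aim of half in each order.

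**The case against.** The strongest reply is that silence is not a defect in execution. A random number generated on the day cannot be foreseen, and knowing the odd/even key reveals nothing before the draw. Nothing allows a redraw, and section 8.4 requires any identified deviation to be documented. All of this stands. It does not close the gap, because with no recorded number an override could not be identified in the first place. The protocol also refers to a separate Schedule of Events (Appendix 2), which was not available here.

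The second reply is that the rest rule limits any residual. That stands too. The assumed average residual is 0.3 × 2 + 0.7 × 0.5 = 0.95 points, more than the whole 0.9-point target, so the larger figures are at the severe end. The limit is not complete, since the twenty-minute branch of Step 4 does not itself require readings to be back at baseline.

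The third reply is that the motive is not one-sided. Section 7.3 removes incomplete pairs in either order, a decliner's Nor_6MWT result still reaches the medical team, and staff might equally start a frail patient on the gentler walk. This stands, and it leaves the direction unknown. A negative bias would shrink a Max-greater-than-Nor difference; a positive one would inflate it.

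A reader might infer that staff can see the order in advance, or that linking order to severity necessarily biases the contrast even after adjusting for order. The documents support neither. The first has no basis in the text. The second needs actual selective ordering together with one of the specific conditions shown in the working, and the plan has no order adjustment in any case.

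**Conclusion.** The point holds as a gap in safeguards and audit trail, not as evidence of bias. Used as written, with a fair number, the draw gives no bias. If draws were selectively repeated or overridden, the planned unadjusted paired comparison would be exposed to any walk-1 residual. An order term would remove a residual common to all patients, but not one that differs by severity, and unequal sequences combined with a severity-dependent test effect would also leave some bias.

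The size cannot be established from the documents. Frail share, residuals, redraw rate and SD are all assumed. Across the scenarios worked here the bias runs from nil to about a third of the assumed target unadjusted, and under a fifth adjusted, in either direction. Most of the milder scenarios are small next to 0.30 SD. The case for change rests on the low cost and on being able to show that the order was random, and does not depend on any one of these figures.

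**What to change.** Replace the on-the-day draw in section 5 with the following:

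- An order list generated in advance by someone who does not run visits, such as an academic collaborator, in blocks of varying size.
- A separate list for each of the two locations in section 6, since a single numbered series opened in turn does not work across two hospitals. Each list should be long enough to cover any replacement of removed patients.
- Orders held in a locked electronic form or numbered sealed envelopes, with the next one revealed only after written consent and the Step 1 baseline have been recorded.
- A log of date, time and study ID at each reveal, and a report of any departure from the listed order.
- A period (order) term in the paired analysis, for example the equal-weight mean of the two sequence means of D.

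The cost is about an hour of preparation and a list and log kept at each location. No extra patients, visits or staff are needed.
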